## Twenty-Four-Month Clinical Comparison of Two Bulk-Fill and Microhybrid Composite Restorations

### Materials and Methods

#### Patient selection

The Research Ethics Committee of Tokat Gaziosmanpasa University (Tokat, Turkey) approved the study, and a group of patients who were seeking routine dental care was subsequently recruited by the Department of Restorative Dentistry, Faculty of Dentistry, Tokat Gaziosmanpasa University, and screened for inclusion in the study. A total of 25 patients who needed at least three similar Class II restorations were asked to participate in the study.

The inclusion criteria were as follows: Patient in need of restoration of caries lesion (diagnosed with bitewing radiograph and clinical examination); teeth in need of restoration to be first or second molars or permanent premolars; at least three Class II restorations required in each patient and the number of restorations of each material to be equal in each patient; the antagonist and adjacent tooth in contact; pulp vitalized and free of painful symptoms; teeth involved not to have undergone direct pulp capping; no history of hypersensitivity in the teeth to be restored; permanent dentition; good oral health and absence of periodontal disease; patients not to have suffered from systemic diseases or allergies; and absence of deleterious habits, xerostomia, and bruxism.

Specific exclusion criteria were as follows: Fewer than 20 teeth; history of existing tooth sensitivity; known allergy to resin-based materials or any of the other materials used in this study; pregnancy or breastfeeding; chronic use of anti-inflammatory drugs, analgesic, and/or psychotropic drugs; non-vital teeth; abutment teeth for fixed or removable prostheses. The average age of patients was 20 years (range, 18–22 years). All patients participated voluntarily and were required to provide written informed consent. The purpose and implications of the treatment were discussed with the patients, and all participants consented to participate voluntarily in the study by signing a term of informed consent. The participants were informed that they were free to withdraw from the trial without justification at any stage of the research.

The dental cavities were at least 3 mm deep. A bitewing radiograph of each tooth was taken using an X-ray device. The operator measured the height and depth of the proximal and occlusal cavity boxes with a periodontal probe (Satin Steel Handle; mm, Hu-Friedy, Chicago, IL, USA). One experienced dentist placed all 75 restorations. The filling materials and adhesives (**Table 1**), bulk fill materials [Sonic Fill (Kerr), x-tra fil (VOCO)] or microhybrid composite (Filtek Z-250 3M ESPE), were used according to the manufacturer's instructions and were randomized over these two cavity groups by using a table of random numbers. Before treatment, initial periapical radiographs of the teeth to be treated were taken and vitality test scores were recorded.

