#### Restorative procedure

All restorations (25 for each restorative material) were performed by the same operator to ensure consistency ([name]). Twenty-five patients received a total of 75 restorations. As such, each patient received three Class II restorations randomly: one with Sonic Fill (Kerr); a conventional viscosity composite, Filtek Z-250 (3M ESPE);

and the other with x-tra fil (VOCO), a high-viscosity bulk-fill composite. Local anesthesia was applied for patients who complained of pain or sensitivity. The cavity preparation was made by using a spherical diamond bur (Meisinger Dental Burs, Hager and Meisinger GmbH, Neuss, Germany) on a high-speed air turbine. Infected dentin in the cavity was removed by carbide round burs used with a low-speed handpiece, and no bevel was prepared. Discolored but hard dentine was left in place at the cavity floor. The cavities were designed according to the principles of minimally invasive dentistry. None of the cavity preparations involved one or more cusps. All of the gingival margins included sound enamel. The operative field was cleaned with an air/water spray, gently air-dried, and then carefully isolated with cotton rolls and suction. The outline shape of the preparations was limited to the removal of caries; as such, no additional retention and bevel was prepared. For each restoration, the tooth type (molar/premolar) and cavity type (number of restored surfaces) were recorded. All patients received oral hygiene instructions and a professional tooth cleaning before initiating the restorative intervention. No liner or base was used.

An ivory type matrix system (Hahnenkratt, Königsbach-Stein, Germany) and wooden wedges were used. To remove water, the cavities were rinsed for 10 s and air-dried for 5 s. Three adhesive systems were used: OptiBond™ XTR (Kerr), Solobond M (VOCO), Adper Single Bond 2 (3M ESPE). The adhesives were applied following the manufacturer's instructions (**Table 1**). All light-curing procedures were performed with the same LED-curing unit (Model BUILT-IN C, Guilin Woodpecker Medical Instrument Co., Ltd., Guilin, Guangxi, China) operating in a continuous mode while emitting a light-intensity of 1200 mW/cm^2 according to the manufacturers' recommended polymerization times. The light was directed perpendicular to the occlusal surface.

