Three different restorative resins were placed in each patient, resulting in a total of 75 restorations; 25 of the preparations were restored using the bulk-fill resin composite Sonic Fill (Kerr, Orange, CA, USA) (n = 25), 25 of them were restored with Filtek Z-250 (3M ESPE, St Paul, MN, USA) (n = 25), and 25 of them were restored with x-tra fil (VOCO, Cuxhaven, Germany), according to the manufacturers' instructions (**Table 1**). The Filtek Z-250 restorative material was applied using an incremental filling technique, beginning at the gingival wall. The increments, not exceeding 2 mm in thickness, were added to complete the proper anatomical form. Each increment was polymerized for 20 seconds. The x-tra fil restorative material was placed in bulk up to 4 mm in thickness and cured for 10 seconds with the same curing unit. The other bulk-fill resin composite material, Sonic Fill, was applied to the bonded cavities with sonication (SonicFill Handpiece, Kerr) and photo-polymerized for 40 s according to the manufacturer's instructions. The randomization of restorative material was done using a table of random numbers.

After removal of the matrix system, the restorations on the teeth in all groups were light-cured for a further 20 s from the buccal, lingual, and occlusal aspects. The cotton rolls were then removed, and occlusion and articulation were checked and adjusted. The surface of the teeth was finished with fine-grit diamond instruments (Diatech, Coltene, Switzerland), polishing disks (Sof-Lex, 3M-ESPE, MN, USA), and rubber polishing instruments (One Gloss, Shofu, Kyoto, Japan). Water-cooling was used throughout the finishing procedures. We used abrasive strips (3M ESPE, St. Paul, MN, USA) on the proximal surfaces when necessary. We checked the quality of the interproximal contact and the cervical adaptation by means of dental flossing and bitewing radiographs. The clinical procedure of tooth preparation and placement of restorations was performed by the same operator.

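### Allocation is described only as a random-number table, so the one unblinded operator who prepares and fills every tooth could match cavities to materials; separately, one inclusion criterion is known only after allocation

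*Combined protocol and SAP*

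**What the plan says.** - **Allocation.** Restorative procedure states: "The randomization of restorative material was done using a table of random numbers". Patient selection also names the random-number table and refers to two groups of cavities that it never defines. Neither section says who held the table, whether it was hidden, when a tooth's material became known, or how teeth were ordered. Patients needed three or more restorations and each received exactly three; no rule says which three.
- **Operator.** One dentist prepared and restored all 75 teeth. Patient selection adds: "The operator measured the height and depth of the proximal and occlusal cavity boxes with a periodontal probe". Restorative procedure gives each material its own placement: one with a sonic handpiece, one in increments of at most 2 mm, one in bulk up to 4 mm.
- **Cavity features.** Patient selection reports "The dental cavities were at least 3 mm deep". Restorative procedure reports "None of the cavity preparations involved one or more cusps" and "All of the gingival margins included sound enamel". None of these is in the inclusion or exclusion list.
- **Listed criteria.** The inclusion list has "at least three Class II restorations required in each patient and the number of restorations of each material to be equal in each patient" and "teeth involved not to have undergone direct pulp capping".
- **Blinding.** Periods and evaluation criteria says the two evaluators were not told which material was in which tooth. It makes no such claim for the operator.
- **Counts.** 25 patients asked, 25 treated, 75 restorations, 25 per material. There is no account of teeth prepared but not used.

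**The concern.** Every patient receives all three materials, so patient characteristics are balanced by design. What remains for randomization to protect is which tooth within the mouth receives which material. That holds only if the teeth and their order are fixed before the material is known, and the plan describes nothing that secures this. The person who cuts and measures each cavity, and so knows best which is difficult, also places the material and cannot be blind to it. If the table was open, the operator could give a harder or easier cavity to a chosen material. Blinded scoring at recall would then record, without error, a difference that came from the teeth.

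The equal-numbers inclusion criterion is a separate defect. It describes the outcome of allocation and placement, not the patient at screening. Read literally, it removes a patient after randomization if one of the three teeth cannot be completed as allocated.

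**Working it through.** **1. The plan's own count.** 25 patients × 3 materials = 75 restorations, and 75 / 3 = 25 per material. This reproduces. The plan states no sample-size or power figure.

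**2. What is known when.**

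| Item | Listed criterion? | When it can be known |
|---|---|---|
| Depth of at least 3 mm | No, a reported feature | Measured in the cut cavity; partly foreseeable on bitewing |
| No cusp involved | No, a reported feature | Confirmed after preparation |
| Gingival margin in sound enamel | No, a reported feature | Confirmed after preparation; partly foreseeable on bitewing |
| No direct pulp capping | Yes | At screening if read as dental history; a new exposure only during caries removal |
| Equal number of each material | Yes | Only after allocation and placement |

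**3. Steering (all inputs assumed).** In each patient one tooth has a 30% risk of a Bravo score and the other two have 10%. There is no true difference between materials. In a fraction f of patients the difficult tooth is kept away from one favoured material.

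- P(difficult tooth in favoured material) = (1 − f)/3
- P(difficult tooth in each other material) = [1 − (1 − f)/3]/2
- Risk = 10% + 20% × that probability

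| f | Favoured | Each other | Expected in 25 restorations |
|---|---|---|---|
| 0 | 10 + 20 × 1/3 = 16.7% | 16.7% | 4.2 v 4.2 |
| 0.5 | 10 + 20 × 1/6 = 13.3% | 10 + 20 × 5/12 = 18.3% | 3.3 v 4.6 |
| 1 | 10 + 0 = 10% | 10 + 20 × 1/2 = 20% | 2.5 v 5.0 |

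A second model gives a similar picture. It assumes standard normal tooth severity, an odds ratio of 2 per standard deviation, about 17% non-Alpha overall, and the easiest tooth going to one material. Steering in 10%, 25%, 50% and 100% of patients gives 16.3 v 17.4%, 15.2 v 17.9%, 13.4 v 18.8% and 9.8 v 20.6%.

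**4. Dropping a patient.** If k patients are dropped, each material loses k teeth and has 25 − k left. The comparison is biased only if dropping depends on which tooth drew which material.

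**5. The third allocation.** With one of each material per patient, the last allocation follows from the first two. Once the three teeth are fixed, only one tooth and one material remain, so nothing can be rematched. The knowledge matters only if that tooth can be swapped for another or withdrawn.

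**6. Loss after preparation (assumed per-tooth rate q).** If the cavity features did act as conditions for using a tooth, the share of patients losing a full set is 1 − (1 − q)^3, and the chance that all 75 teeth pass is (1 − q)^75.

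| q | Patients losing a full set | All 75 pass |
|---|---|---|
| 1% | 3.0% | 47% |
| 2% | 5.9% | 22% |
| 5% | 14.3% | 2.1% |
| 10% | 27.1% | 0.04% |

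**The case against.** The strongest reply is that the plan is silent rather than wrong. If someone other than the operator held the list and revealed each material after preparation, most of the risk goes. This stands as a limit on wording: concealment is not described, which is not the same as absent. It does not remove the point, because the method as written allows steering and a better one is cheap.

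Second, the cavity features are past-tense descriptions, not eligibility rules, and no text says that a tooth was rejected for failing one. The pulp-capping item can be read as dental history. Bitewing and periapical radiographs gave some advance view. All of this stands. A reader might infer that teeth passed a set of eligibility checks after allocation was known; the documents do not support that. The matching concern does not need it, only that difficulty is best seen by the person who places the material.

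Third, patients were approached because their restorations were similar, which narrows the spread of difficulty within a mouth. That reduces the possible size, but similarity is not defined.

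Fourth, the equal-numbers item may be no more than a loosely placed description of the design. That is plausible, and restating it as an allocation rule costs nothing.

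**Conclusion.** The point holds as a weakness of the described method and should be fixed. A bare random-number table, no stated order or choice of teeth, and one unblinded operator who prepares, measures and fills leave the within-patient matching of teeth to materials unprotected. The equal-numbers criterion is misplaced, whatever was done about concealment.

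The documents do not fix the size. On the assumed 30% and 10% risks, steering in half of patients creates a spurious gap of 18.3 − 13.3 = 5 percentage points, or 1.25 restorations in 25. Steering in every patient creates 10 points, or 2.5 restorations.

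Three stronger readings are not supported:

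- **That a third of allocations being deducible lets the operator steer them.** With fixed teeth, it does not.
- **That dropping patients is as serious a route as matching.** It removes one tooth per material and biases only under the condition in step 4.
- **That 75 of 75 conforming teeth points to unreported exclusions.** The failure rates are assumed, the features are not listed criteria, and the text reports 25 asked and 25 treated with no patient dropped.

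The risk is open; neither bias nor exclusion has been shown.

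**What to change.** 1. At screening, select the three study teeth by a fixed rule when a patient has more than three candidates, and number them in a fixed order, for example by tooth number.
2. Have someone other than the operator prepare each patient's random order of the three materials in a sequentially numbered opaque envelope. Open the part for a tooth only after its cavity has been prepared, measured and recorded.
3. Remove the equal-numbers item from the inclusion list and state it as an allocation rule of one restoration of each material per patient. Analyse every tooth whose allocation was opened, including teeth from incomplete sets.
4. Define the two cavity groups or delete the reference to them.

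If placement is already complete, state who held the table and how and when each material was revealed. Tabulate cavity depth, tooth type and number of surfaces by material; all were measured or recorded. Balance in that table would be reassuring but could not rule out steering on features that were not recorded.

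The cost is one protocol paragraph and 25 envelopes, a slight delay at the chair because the material is known only after preparation, and possibly a few incomplete sets. The planned between-material comparison, a Pearson chi-square test, does not require complete sets.

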#### Restorative procedure

All restorations (25 for each restorative material) were performed by the same operator to ensure consistency ([name]). Twenty-five patients received a total of 75 restorations. As such, each patient received three Class II restorations randomly: one with Sonic Fill (Kerr); a conventional viscosity composite, Filtek Z-250 (3M ESPE);

and the other with x-tra fil (VOCO), a high-viscosity bulk-fill composite. Local anesthesia was applied for patients who complained of pain or sensitivity. The cavity preparation was made by using a spherical diamond bur (Meisinger Dental Burs, Hager and Meisinger GmbH, Neuss, Germany) on a high-speed air turbine. Infected dentin in the cavity was removed by carbide round burs used with a low-speed handpiece, and no bevel was prepared. Discolored but hard dentine was left in place at the cavity floor. The cavities were designed according to the principles of minimally invasive dentistry. None of the cavity preparations involved one or more cusps. All of the gingival margins included sound enamel. The operative field was cleaned with an air/water spray, gently air-dried, and then carefully isolated with cotton rolls and suction. The outline shape of the preparations was limited to the removal of caries; as such, no additional retention and bevel was prepared. For each restoration, the tooth type (molar/premolar) and cavity type (number of restored surfaces) were recorded. All patients received oral hygiene instructions and a professional tooth cleaning before initiating the restorative intervention. No liner or base was used.

An ivory type matrix system (Hahnenkratt, Königsbach-Stein, Germany) and wooden wedges were used. To remove water, the cavities were rinsed for 10 s and air-dried for 5 s. Three adhesive systems were used: OptiBond™ XTR (Kerr), Solobond M (VOCO), Adper Single Bond 2 (3M ESPE). The adhesives were applied following the manufacturer's instructions (**Table 1**). All light-curing procedures were performed with the same LED-curing unit (Model BUILT-IN C, Guilin Woodpecker Medical Instrument Co., Ltd., Guilin, Guangxi, China) operating in a continuous mode while emitting a light-intensity of 1200 mW/cm^2 according to the manufacturers' recommended polymerization times. The light was directed perpendicular to the occlusal surface.

Three different restorative resins were placed in each patient, resulting in a total of 75 restorations; 25 of the preparations were restored using the bulk-fill resin composite Sonic Fill (Kerr, Orange, CA, USA) (n = 25), 25 of them were restored with Filtek Z-250 (3M ESPE, St Paul, MN, USA) (n = 25), and 25 of them were restored with x-tra fil (VOCO, Cuxhaven, Germany), according to the manufacturers' instructions (**Table 1**). The Filtek Z-250 restorative material was applied using an incremental filling technique, beginning at the gingival wall. The increments, not exceeding 2 mm in thickness, were added to complete the proper anatomical form. Each increment was polymerized for 20 seconds. The x-tra fil restorative material was placed in bulk up to 4 mm in thickness and cured for 10 seconds with the same curing unit. The other bulk-fill resin composite material, Sonic Fill, was applied to the bonded cavities with sonication (SonicFill Handpiece, Kerr) and photo-polymerized for 40 s according to the manufacturer's instructions. The randomization of restorative material was done using a table of random numbers.

After removal of the matrix system, the restorations on the teeth in all groups were light-cured for a further 20 s from the buccal, lingual, and occlusal aspects. The cotton rolls were then removed, and occlusion and articulation were checked and adjusted. The surface of the teeth was finished with fine-grit diamond instruments (Diatech, Coltene, Switzerland), polishing disks (Sof-Lex, 3M-ESPE, MN, USA), and rubber polishing instruments (One Gloss, Shofu, Kyoto, Japan). Water-cooling was used throughout the finishing procedures. We used abrasive strips (3M ESPE, St. Paul, MN, USA) on the proximal surfaces when necessary. We checked the quality of the interproximal contact and the cervical adaptation by means of dental flossing and bitewing radiographs. The clinical procedure of tooth preparation and placement of restorations was performed by the same operator.

### **Periods and evaluation criteria**

One week after restoration placement (baseline), patients were recalled and restorations were examined clinically. Direct clinical evaluation of restorations was performed using the USPHS criteria (**Table 2**) by two independent investigators ([name] and [name]) using mirrors, probes, and bitewing radiographs and scored as Alpha, Bravo, or Charlie. Alpha corresponded to excellent, Bravo to clinically acceptable, and Charlie to clinically unacceptable results (**Table 2**). Patients were recalled at 6, 12, and 24 months for assessments of the restorations, using the same criteria as at baseline. At each recall, the same two calibrated evaluators, who were blinded to the restoratives used for cavities and patients, examined the restorations. To ensure a double-blind study, the evaluators were not informed about which filling material had been used on which teeth. When disagreement occurred during the evaluation, the final decision was made by the consensus of both examiners. All evaluations were carried out under a dental operating light, using flat-surfaced mouth mirrors and dental explorers. Postoperative sensitivity was assessed by blowing a stream of compressed air for three seconds at a distance of 2 to 3 cm from the restoration under isolation from the adjacent teeth with gauze and by moving the probe over the restored tooth surface.

The statistical analyses were carried out with the IBM SPSS version 22.0 software package (SPSS, Chicago, IL, USA). The restoration groups for each category were compared using the Pearson chi-square test, and the Cochran Q-test was used to compare the changes across different time points within each restorative material ( $p < 0.05$ ).

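### The materials are compared with a Pearson chi-square test that ignores the within-patient matching, so true differences are easier to miss if restorations in the same mouth are correlated

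*Combined protocol and SAP*

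**What the plan says.** Patient selection requires "at least three Class II restorations required in each patient and the number of restorations of each material to be equal in each patient". Restorative procedure confirms that this was done: "Twenty-five patients received a total of 75 restorations", "each patient received three Class II restorations randomly", and "Three different restorative resins were placed in each patient, resulting in a total of 75 restorations". Each patient therefore contributes one matched triplet.

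The statistics paragraph at the end of Periods and evaluation criteria gives two analyses. Between materials: "The restoration groups for each category were compared using the Pearson chi-square test". Over time: "the Cochran Q-test was used to compare the changes across different time points within each restorative material". The threshold is 0.05. No other between-material method is named: no McNemar or Friedman test, and no mixed model, GEE or other allowance for patient.

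**The concern.** Pearson's chi-square treats the 75 restorations as if they came from 75 unrelated patients. In fact each patient serves as his or her own control. What the three restorations share (hygiene, caries risk, occlusion) cancels out of a within-patient comparison, but Pearson leaves it in the error term. The plan uses a matched method for repeated visits and does not carry the same reasoning over to three restorations in one mouth.

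At stake is the trial's main answer, because this is the only test that compares the materials. A test that understates the evidence makes a non-significant result more likely. In this setting such a result could be read as the bulk-fill materials performing like the microhybrid comparator.

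**Working it through.** **Inputs from the document.** 25 patients, three materials, one restoration of each per patient, scores Alpha/Bravo/Charlie, threshold 0.05. The total reproduces: 25 × 3 = 75. The plan gives no power calculation, expected rates or within-patient correlation, so there is no design figure to reproduce beyond that count. Rates and correlations below are assumptions, and the outcome is taken as Alpha versus not Alpha.

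**Step 1: large-sample size of the Pearson test.** Let each material have the same non-Alpha probability p, and let r be the correlation between two restorations in one patient. The within-patient difference between two materials has variance 2p(1−p)(1−r). Pearson uses 2p(1−p). Under no difference the Pearson statistic therefore behaves as (1−r) times a chi-square on 2 df. Its true size is P(χ²₂ > 5.991/(1−r)). The 2-df tail is exp(−x/2), so this equals 0.05 raised to the power 1/(1−r).

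| r | 1/(1−r) | true size of nominal 5% test |
|---|---|---|
| 0 | 1.00 | 0.050 |
| 0.1 | 1.11 | 0.036 |
| 0.2 | 1.25 | 0.024 |
| 0.3 | 1.43 | 0.014 |
| 0.5 | 2.00 | 0.0025 |

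**Step 2: simulation at the actual sample size.** 40,000 trials per cell, 25 triplets, normally distributed latent patient effect, large-sample p-values for both tests. Size is at 20% non-Alpha for all three materials; power is at 20/20/50%.

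| r (approx.) | Pearson size | Cochran Q size | Pearson power | Cochran Q power |
|---|---|---|---|---|
| 0 | 0.047 | 0.050 | 0.65 | 0.65 |
| 0.10 | 0.033 | 0.050 | 0.66 | 0.70 |
| 0.23 | 0.021 | 0.050 | 0.66 | 0.77 |
| 0.37 | 0.009 | 0.048 | 0.66 | 0.85 |
| 0.56 | 0.002 | 0.046 | 0.65 | 0.94 |

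Other assumed rates give the same picture. At 15/15/45%, Pearson has 71–72% power, against 70%, 78% and 84% for Cochran's Q at r of 0, 0.17 and 0.31. At 10/10/35%, Pearson has about 63%, against 63%, 70% and 77% for Q at zero, moderate and higher correlation.

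**Step 3: one constructed data set.** Of 25 patients, 15 have no non-Alpha score, 4 have all three, 5 have only material C and 1 has only material B. The totals are 4, 5 and 9, with mean 6. The sum of squared deviations is 4 + 1 + 9 = 14, and both statistics have this numerator.

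- Pearson: the pooled rate is 18/75 = 0.24, the denominator is 25 × 0.24 × 0.76 = 4.56, the statistic is 14/4.56 = 3.07, and p = 0.215.
- Cochran's Q: 2 × (3 × (16 + 25 + 81) − 18²) / (3 × 18 − (4 × 9 + 6 × 1)) = 2 × 42/12 = 7.0, and p = 0.030.
- Exact within-patient version: the 6 discordant patients each have one non-Alpha score, which could fall on any of three materials, giving 3⁶ = 729 equally likely layouts. Splits at least as extreme as 5/1/0 number 36 (5/1/0 in any order) + 3 (6/0/0) = 39, so p = 39/729 = 0.053.

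Pearson's p-value is about four times the exact matched one. The large-sample Q is somewhat optimistic with so few discordant patients.

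**The case against.** The strongest reply is that the error is on the safe side. With positive correlation the true error rate is below 5%, so a significant Pearson result is not undermined, and at zero correlation nothing material is lost. This is correct and limits the harm to missed differences. It does not make the choice harmless where a non-significant result may be read as similar performance.

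The size also rests on assumptions. Neither the correlation nor the rates come from the document, and the power figures concern differences of 25 to 30 percentage points. At a correlation near 0.17 the gain is only about 6 to 7 points of power. This stands.

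Part of Pearson's conservatism comes from sparse data and not from lost matching. At a 10% rate and zero correlation its size is already about 0.036. At a 2% rate both tests are far below nominal: 0.015 each at zero correlation, and 0.007 against 0.008 at about 0.16. Cochran's Q does not hold 5% everywhere either; it falls to 0.029 at a 10% rate with correlation near 0.5. For categories where almost every score is Alpha, changing the test will therefore change little.

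Finally, the power figures are for the large-sample Cochran's Q. The Friedman test and the exact versions recommended below were not simulated, and exact McNemar is itself conservative with few discordant pairs. The exact versions may gain less than the figures shown.

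**Conclusion.** The concern holds. The design is a complete within-patient block, and the only between-material test assumes independent restorations. If within-patient correlation is positive, which is plausible for three restorations in one mouth, the Pearson p-values are too large. Over assumed correlations of 0.1 to 0.3 the large-sample size drops to between 0.036 and 0.014. In the scenarios examined, correlations from about 0.1 to 0.37 cost roughly 4 to 19 percentage points of power. The direction depends only on positive correlation; the amount depends on rates and correlations that the plan does not give. Type I error is not inflated under that assumption. A non-significant Pearson result is weak evidence that the materials perform alike.

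**What to change.** Replace the Pearson test with one blocked on patient. For each category and visit, use either the Friedman test on the ordered Alpha/Bravo/Charlie scores or Cochran's Q on Alpha versus not Alpha across the three materials. State in advance which is used, and take p-values from within-patient permutation. For pairs of materials, use exact McNemar or exact signed-rank tests within patient, with a stated rule for the three comparisons (for example, only after a significant three-material test, or Holm adjustment). Report the paired difference in percent Alpha with a 95% confidence interval, so that a non-significant result is not taken as equivalence.

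Say how patients with fewer than three evaluable restorations at a recall are handled. Complete-block Cochran's Q and Friedman tests drop them. An ordinal mixed model or GEE clustered on patient would keep them and could serve as a supporting analysis.

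The cost is a few sentences in the statistics paragraph. Because the document is written in the past tense, it may also mean re-analysing scores already collected. No extra patients, visits or measurements are needed.
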